8.6.12 Part B, Visit 7 (~Month 11/Week 44 ± 7 days)—Injection #3

The decision to conduct Part B extension of the study will be based on the results of the interim analysis (see [Section 9.2.4](#)).

Predose:

1. Informed consent and assent (may be signed up to 28 days prior to Part B, Visit 7)
2. Query subject or parent “How have you felt in the last two weeks?” or “How has your child felt in the last two weeks?” Complete [Table 4](#)
3. Vital signs - measured prior to any blood draws
4. AE and concomitant medications assessments
5. Physical Examination—directed

6. Tanner stage
7. Height and weight
8. X-ray of non-dominant hand and wrist
9. Clinical laboratory assessments (hematology, chemistry)
 - a. Hematology and chemistry parameters as per [Appendix 13.1](#)
 - b. Serum lipids, fasting for ≥ 8 hours (water permitted)
10. Urine for urinalysis, performed using dipstick supplied by Sponsor
11. Urine pregnancy test, females only
NOTE: Results must be negative prior to receiving Injection #3)
12. Blood samples for basal LH, FSH, testosterone/estradiol concentrations PRIOR to the GnRH α stimulation
13. Blood sample for basal serum leuprolide concentrations PRIOR to the GnRH α stimulation
14. GnRH α stimulation: aqueous leuprolide acetate 20 $\mu\text{g}/\text{kg}$ body weight administered SC
15. Blood samples for LH, FSH, testosterone/estradiol concentrations 30 \pm 5 minutes AFTER the GnRH α stimulation test

Study Drug Administration:

16. Pharmacy - prepare study drug for injection (see Pharmacy Manual for complete instructions)
 - a. Remove kit from refrigerator, at least 30 minutes prior to planned administration and allow the study drug to reach room temperature
 - b. Start mixing process with the product kit within ≤ 30 minutes prior to the injection time.
17. Apply topical or local anesthetic (per Investigator discretion) to injection site prior to planned injection time; record medication, dose, route, and time
18. Administer third injection of study drug

Postdose:

1. Final AE assessment prior to subject discharge from clinic
2. Schedule/confirm next visit

8.6.13 Telephone Contact 3 (14 days \pm 2 days) Post Injection #3

1. Query subject or parent “How have you felt in the last two weeks?” or “How has your child felt in the last two weeks?” Complete [Table 4](#)

8.6.14 Part B, Visit 8 (~Month 15/Week 60 \pm 7 days)

1. Query subject or parent “How have you felt in the last two weeks?” or “How has your child felt in the last two weeks?” Complete [Table 4](#)
2. Vital signs - measured prior to any blood draws
3. AE and concomitant medications assessments
4. Physical Examination—directed
5. Tanner stage
6. Height and weight
7. Blood samples for basal LH, FSH, testosterone/estradiol concentrations
8. Blood sample for basal serum leuprolide concentrations
9. Schedule/confirm next visit

8.6.15 Part B, Visit 9 (~Month 16/Week 64 ± 7 days)—Injection #4

Predose:

1. Query subject or parent “How have you felt in the last two weeks?” or “How has your child felt in the last two weeks?” Complete [Table 4](#)
2. Vital signs - measured prior to any blood draws
3. AE and concomitant medications assessments
4. Physical Examination—directed
5. Tanner stage
6. Height and weight
7. X-ray of non-dominant hand and wrist
8. Clinical laboratory assessments (hematology, chemistry) as per [Appendix 13.1](#)
9. Urine for urinalysis, performed using dipstick supplied by Sponsor
10. Urine pregnancy test, females only
NOTE: Results must be negative prior to receiving Injection #4)
11. Blood samples for basal LH, FSH, testosterone/estradiol concentrations PRIOR to the GnRHa stimulation
12. Blood sample for basal serum leuprolide concentrations PRIOR to the GnRHa stimulation
13. GnRHa stimulation: aqueous leuprolide acetate 20 µg/kg body weight administered SC
14. Blood samples for LH, FSH, testosterone/estradiol concentrations 30 ± 5 minutes AFTER the GnRHa stimulation test

Study Drug Administration:

15. Pharmacy - prepare study drug for injection (see Pharmacy Manual for complete instructions)
 - a. Remove kit from refrigerator, at least 30 minutes prior to planned administration and allow the study drug to reach room temperature
 - b. Start mixing process with the product kit within ≤ 30 minutes prior to the injection time.
16. Apply topical or local anesthetic (per Investigator discretion) to injection site prior to planned injection time; record medication, dose, route, and time
17. Administer third injection of study drug

Postdose:

18. Final AE assessment prior to subject discharge from clinic
19. Schedule/confirm next visit

8.6.16 Telephone Contact 4 (14 days ± 2 days) Post Injection #4

1. Query subject or parent “How have you felt in the last two weeks?” or “How has your child felt in the last two weeks?” Complete [Table 4](#)

8.6.17 Part B, Visit 10 (~Month 20/Week 76 ± 7 days)

1. Query subject or parent “How have you felt in the last two weeks?” or “How has your child felt in the last two weeks?” Complete [Table 4](#)
2. Vital signs - measured prior to any blood draws

3. AE and concomitant medications assessments
4. Physical Examination—directed
5. Tanner stage
6. Height and weight
7. Blood samples for basal LH, FSH, testosterone/estradiol concentrations
8. Blood sample for basal serum leuprolide concentrations
9. Schedule/confirm next visit

8.6.18 Part B, Visit 11 (~Month 21/Week 80 ± 7 days)—End of Treatment or Early Discontinuation

1. Query subject or parent “How have you felt in the last two weeks?” or “How has your child felt in the last two weeks?” Complete [Table 4](#)
2. Vital signs - measured prior to any blood draws
3. AE and concomitant medications assessments
4. Physical Examination—complete
5. Tanner stage
6. Height and weight
7. X-ray of non-dominant hand and wrist
8. Urine pregnancy test, females only
9. Clinical laboratory assessments (hematology, chemistry) as per [Appendix 13.1](#)
10. Urine for urinalysis, performed using dipstick supplied by Sponsor
11. Blood samples for basal LH, FSH, testosterone/estradiol concentrations PRIOR to the GnRHa stimulation
12. Blood sample for basal serum leuprolide concentrations PRIOR to the GnRHa stimulation
13. GnRHa stimulation: aqueous leuprolide acetate 20 µg/kg body weight administered SC
14. Blood samples for LH, FSH, testosterone/estradiol concentrations 30 ± 5 minutes AFTER the GnRHa stimulation test

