enter Part B extension. Injections #3 and #4 will be administered in 5-month intervals after Injection #2 in Part A. The dosing interval will be dependent on emerging data from Part A. Subjects will return to the clinic periodically up to approximately an additional 10 months from start of Part B for efficacy, safety and PK assessments.

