8.1.1 Duration of Study

In Part A, after a 28-day screening period, each subject will participate in the study for 48 weeks. Six months after Injection #1 in Part A, subjects will receive Injection #2 of the study drug. There will be a total of 7 study visits during Part A for a total duration of approximately 12 months.

Part A of the study is expected to take up to 24 months from first subject first visit (FSFV) to last subject last visit (LSLV), if Part B is not conducted.

After the interim analysis, if the DSMB and the Sponsor make the decision to conduct Part B of the study then all currently enrolled eligible subjects and all newly enrolled subjects will receive a total of 4 injections of the study drug. Subjects who have gone beyond the Month 11 visit will not be considered eligible to participate in Part B extension as they would be considered to be out-of-window for Injection #3.

If Part B of the study is invoked, the study length (for both Parts A and B) will be expected to be extended for approximately 10 more months for a total of approximately 34 months from FSFV (Injection #1) to LSLV. With the addition of Part B, commitment of each subject in the study will increase from 12 months to 21 months.

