8.5.6.1 Reporting of Serious Adverse Events

When an SAE or SUSAR occurs, the Investigator or designee must log into the electronic data capture (EDC) system and complete the SAE Report form within 24 hours of first becoming aware of the SAE. All SAEs (including deaths of any cause) that occur after administration of study drug and within 6 months after the last administration of study drug in Part A, or within 5 months after the last administration of study drug in Part B is invoked, whether or not considered related to study drug must be reported. The Investigator must also report SAEs to the Sponsor or representative (contract research organization [CRO]) and to the IRB/IEC as required by local and national laws. The Investigator must maintain documentation of all communications to and from the IRB/IEC. The SAE Report from the site should include date and time of onset, description of event, severity, duration, outcome, etiology, relationship to study drug, action taken and other relevant details as available. The Investigator is also responsible for updating the SAE Report Form as additional information becomes available. The Investigator may be requested for additional follow-up information by the Sponsor or the pharmacovigilance service provider in order to have more complete information for regulatory reporting.

All SAEs/SUSARS will be monitored by the CRO Medical Monitor or pharmacovigilance service provider prior to submission to the regulatory authorities. Events associated with this clinical trial will be recorded in the ELIGARD[®] global safety database that is maintained for reporting and analysis.

The Sponsor will adhere to all AE regulatory reporting requirements in accordance with local regulation and local authorities.

Additional safety instructions will be provided to clinical sites including contact numbers and schedules to report all AEs, SAEs and SUSARs associated with this study.

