9.2.2 Efficacy Evaluations

Primary Efficacy Endpoint

- **Part A:** the percentage of subjects with serum LH concentrations < 4 mIU/mL 30 minutes following an abbreviated GnRHa stimulation test at the Month 6 visit
Leuprolide Acetate 45 mg will be considered effective for the treatment of children with CPP if $\geq 80\%$ of subjects exhibit LH suppression < 4 mIU/mL at Month 6
- **Part B Extension:** the percentage of subjects with serum LH concentrations < 4 mIU/mL 30 minutes following an abbreviated GnRHa stimulation test at the Month 21 visit (5 months after the Injection #4 of leuprolide acetate)

Leuprolide acetate 45 mg will be considered effective for the treatment of children with CPP if $\geq 80\%$ of subjects exhibit LH suppression < 4 mIU/mL at the Month 21 visit (5 months after the last of 4 administrations of the study drug)

NOTE: If Part B extension is conducted, the primary efficacy endpoint for Part A will become a secondary efficacy endpoint of Part B.

Secondary Efficacy Endpoint: Parts A & B

- The percentage of subjects with suppressed serum LH concentrations (< 4 mIU/mL) 30 minutes post GnRHa stimulation test at all assessed time points
- Changes in height velocity (growth rate), and bone age advancement will be evaluated relative to chronological age using descriptive statistics from baseline to end of study
- Changes in physical signs of puberty as measured by changes in Tanner stages from baseline to end of study

Exploratory Assessments: Parts A & B

- Bone age progression will be further evaluated using descriptive statistics and figures at all assessed timepoints. Changes in bone age progression will be described for each individual and for the ITT and PP population over the entire treatment period
- Descriptive statistics will be used to describe changes in physical signs of puberty as measured by changes in Tanner stages at each assessed timepoint. Changes in Tanner staging will be described for each individual and for the ITT and PP population over the entire treatment period.
- The percentage of subjects with LH (< 4 mIU/mL), FSH (< 2.5 mIU/mL), estradiol (< 20 pg/mL) or testosterone (< 30 ng/dL) suppression to prepubertal levels and serum leuprolide levels at all assessed timepoints

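### The Part B primary test is defined at 5 months after Injection #4 but scheduled at 16 weeks, 4 weeks short of the plan's own 5-month interval

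*Protocol*

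**What the plan says.** **Endpoint definition.** Protocol 9.2.2 sets the Part B primary endpoint "at the Month 21 visit (5 months after the Injection #4 of leuprolide acetate"). SAP 8.2.1 gives the same timing, and both documents claim efficacy if at least 80% of subjects are suppressed at Visit 11 (Protocol 9.2, SAP 6.6).

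**Schedule.** Protocol 8.6.15 is headed "Part B, Visit 9 (~Month 16/Week 64 ± 7 days)—Injection #4". Protocol 8.6.17 is headed "Part B, Visit 10 (~Month 20/Week 76 ± 7 days") and Protocol 8.6.18 "Part B, Visit 11 (~Month 21/Week 80 ± 7 days)—End of Treatment or Early Discontinuation". Table 3 of each document repeats these weeks. In those tables the week row carries the ±7-day window; the month row is marked as approximate and has no window.

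**Stated durations.** Protocol 8.1 has Part B subjects returning "up to approximately an additional 10 months from start of Part B", and Protocol 8.1.1 says the "commitment of each subject in the study will increase from 12 months to 21 months". SAP 6.1.2 also gives Part B a further 10 months.

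**The concern.** The month labels agree with the endpoint definition (16 + 5 = 21), but the week labels do not (64 + 20 = 84, not 80). A site cannot meet both. One that tests at Week 84 is 3 weeks past the end of the Visit 11 window (Week 81), and one that stays in the window tests too early. If sites differ, two timings are pooled in one primary percentage.

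Part B exists because, according to Protocol 6.2, the 45 mg dose might not hold LH down for six months yet might do so for five. Loss of suppression late in the interval is therefore the plan's own worry. A test 16 weeks after the dose does not show that suppression lasts to 20 weeks, and if suppression does wane late the error favours the efficacy claim. The basal hormone and leuprolide samples at Visit 10 would also come 4 weeks earlier in their cycle than those at Visit 8, which weakens any comparison between the two 5-month cycles.

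**Working it through.** **1. The week/month convention.** Protocol 8.3.1.1 equates Month 6 with 24 weeks, which is 4 weeks per month. Dividing each week label in SAP Tables 1 and 3 by 4 (the shared Week 44 column counted once) gives:

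| Week | Week ÷ 4 | Month label | Fits |
|---|---|---|---|
| 2, 4, 12, 20, 24 | 0.5, 1, 3, 5, 6 | 0.5, 1, 3, 5, 6 | yes |
| 26, 36, 44, 46, 48 | 6.5, 9, 11, 11.5, 12 | 6.5, 9, 11, 11.5, 12 | yes |
| 60, 64, 66 | 15, 16, 16.5 | 15, 16, 16.5 | yes |
| 76 (Visit 10) | 19 | 20 | no, 4 weeks early |
| 80 (Visit 11) | 20 | 21 | no, 4 weeks early |

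Thirteen of 15 pairs fit exactly. The break lies between Visits 9 and 10, which are 20 − 16 = 4 months apart by month label but 76 − 64 = 12 weeks apart by week label.

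**2. The two 5-month cycles compared.**

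- After Injection #3 (Week 44): Visit 8 at 60 − 44 = 16 weeks, Visit 9 at 64 − 44 = 20 weeks.
- After Injection #4 (Week 64): Visit 10 at 76 − 64 = 12 weeks, Visit 11 at 80 − 64 = 16 weeks.
- Injection #2 to Injection #3 is 44 − 24 = 20 weeks, so the other two 5-month intervals are both 20 weeks.

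**3. Size of the shortfall.** (20 − 16)/20 = 20%. With both windows at their extremes:

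- shortest gap: (80 − 1) − (64 + 1) = 14 weeks = 98 days
- longest gap: (80 + 1) − (64 − 1) = 18 weeks = 126 days

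**4. Does it depend on the 4-week month?** With calendar months of 30.44 days, 98/30.44 = 3.2 and 126/30.44 = 4.1 months, still short of 5. Calendar months would put Month 21 at about Week 91, further from Week 80.

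**5. Length of Part B.** As written, 80 − 44 = 36 weeks = 9 four-week months, against the stated 10. With Visit 11 at Week 84, 84 − 44 = 40 weeks = 10 months.

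**6. After correction.** Visit 10: 80 − 64 = 16 weeks. Visit 11: 84 − 64 = 20 weeks, or 18 to 22 with windows. Both now match the Injection #3 cycle.

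**The case against.** The best case for leaving this alone is that the intended timing is plain. The endpoint definitions and decision rules refer to months or to the visit number, never to weeks, so a careful site would read Month 21 as five months after the last dose. The problem arises only if Part B is invoked. Even then, true 20-week stimulation tests exist at Weeks 44 and 64 and are reported as secondary data, so the 5-month question could still be answered. These limits stand and they hold down the severity. They do not remove the conflict, because the window is attached to the week and the primary claim rests on Visit 11 alone.

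Some supporting evidence is weaker than it looks:

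- Telephone Contact 4 at Week 66 agrees with Injection #4 at Week 64, but it is defined as two weeks after that injection and so is not independent confirmation.
- Protocol 8.5.6.1 asks for SAE reports "within 5 months after the last administration of study drug in Part B is invoked", which fits Week 84. However, a reporting period does not fix a visit date, and Protocol 8.5.6 gives six months without separating the Parts.

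The conclusion needs neither. It rests on the endpoint definition, the 4-week convention, the matching Injection #3 cycle and the stated 10- and 21-month durations.

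Week 84 is itself five months only under the 4-week convention: 20 weeks is 140/30.44 = 4.6 calendar months. That holds equally for the other two 5-month intervals, so it is no argument for Week 80.

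**Conclusion.** The inconsistency is real and sits in the current text of both documents. The Part B primary test is scheduled 16 weeks after Injection #4 (14 to 18 with windows) against a defined 5 months, which is 20 weeks on the documents' own count. It is most probably a slip in the week labels of Visits 10 and 11, not a design choice, but it sets the date of the test that decides the efficacy claim, so it should be fixed.

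The consequence assumes that Part B is invoked and that sites schedule by the week row. The direction of bias assumes that suppression weakens late in the interval; the documents give no data from which to size it. Part A, the interim rule and the sample size are unaffected.

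**What to change.** Set Visit 10 to Week 80 ± 7 days and Visit 11 to Week 84 ± 7 days in Protocol 8.6.17, 8.6.18 and Table 3, and in SAP Table 3. Update the Protocol's contents list, which repeats the old labels. Do this before any subject reaches Visit 10, since a mistimed primary test cannot be repeated later.

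The last two Part B visits move 4 weeks later. No visit or test is added, and the stated 21-month participation does not change. The administrative cost is a protocol amendment, which under Protocol 4.1 and 10.6 needs IRB/IEC approval before use.

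Optionally, the example in SAP 7 comparing five- and six-month dosing could name tests already scheduled at the end of each interval: Month 6 against Months 11 and 16.

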8.6.19 Unscheduled Visits

If additional visits are needed, either during Part A or Part B, the following procedures and evaluations may be performed as deemed appropriate by the Investigator. If the subject is expected to return for subsequent visits the GnRHa stimulation test will be optional, while blood samples for hormones must be collected:

1. Query subject or parent “How have you felt in the last two weeks?” or “How has your child felt in the last two weeks?” Complete [Table 4](#)
2. Vital signs - measured prior to any blood draws
3. AE and concomitant medications assessments
4. Physical Examination—complete
5. Tanner stage
6. Height and weight
7. Urine pregnancy test, females only
8. Clinical laboratory assessments (hematology, chemistry) as per [Appendix 13.1](#)
9. Urine for urinalysis, performed using dipstick supplied by Sponsor
10. Blood samples for basal LH, FSH, testosterone/estradiol concentrations PRIOR to the optional GnRHa stimulation test

11. Blood sample for basal serum leuprolide concentrations PRIOR to the optional GnRHa stimulation test
12. At investigator's discretion: GnRHa stimulation: aqueous leuprolide acetate 20 µg/kg body weight administered SC
13. If GnRH stimulation is performed, blood samples for LH, FSH, testosterone/estradiol concentrations will be collected 30 ± 5 minutes AFTER the GnRHa stimulation
14. Schedule/confirm next visit, if appropriate

8.6.20 Study Termination

The clinical study may be stopped at any time at the discretion of the Sponsor or by regulatory authorities (IRB/IEC or governing competent authority). The clinical study may be stopped if the extent (incidence and/or severity) of emerging effects/clinical endpoints is such that the risk/benefit ratio to the study population as a whole is unacceptable.

Further recruitment in the study or at a particular site(s) may be stopped due to insufficient compliance with the Protocol, ICH-GCP and/or other applicable regulatory requirements, procedure-related problems, or if the number of discontinuations for administrative reasons is too high.

Upon study termination, all site closure activities with the investigator or site staff, as appropriate, will be conducted in accordance with applicable regulations including ICH-GCP and sponsor procedures.

After the completion of the study subjects will be managed for their underlying disease according to the local standard of care, and based on the subject's previous medical history. Continued treatment will not be conducted as part of this protocol.

9. STATISTICAL PLAN

Prior to the database lock, a finalized Statistical Analysis Plan (SAP) will be completed and approved. The SAP will contain a comprehensive explanation of the methodology used in the statistical analyses. The SAP will also contain the rules and data handling conventions that will be used to perform the analyses, and the procedure that will be used to account for missing data.

9.1 Sample Size Determination

To determine the percentage of subjects with suppression of serum LH to < 4 mIU/mL following treatment with leuprolide acetate 45 mg, it is estimated that approximately 40 subjects would be sufficient for assessment of Part A and approximately 27 subjects for Part B, if invoked. Approximately 60 subjects may be enrolled in the study in order to get an appropriate number of assessable subjects.

The sample size was pragmatically determined based on the clinical trial size and response rate of other GnRH antagonists studies in CPP subjects.

The descriptive finding that will conclude efficacy is that ≥ 80% of subjects will exhibit < 4 mIU/mL LH suppression. This is conservative, since the dropout rate is unknown, and it is anticipated that the percent of subjects suppressed is likely to be at least 85%. Thus, 85% suppression or 90% suppression might be reasonably expected. However, the drop out in this

study could be slightly more than 50%, if Part B is invoked, thus depending on whether only Part A is carried out or Part B is invoked, the final available sample size after drop out could vary between 25 and 50 subjects given the planned recruitment of 60 subjects. Suppression to < 4 mIU/mL in approximately 70% of the subjects is considered to be clinically important if the full expectations of all drop-out are completed. Thus, the study is thought to have a sufficient number of subjects. If 85% of subjects enrolled are found to be suppressed we would expect a lower 95% one sided confidence interval under a fully realized drop out scenario (ie, 25 final subjects) of slightly more than 70%.

9.2 Statistical Methods

The purpose of this study is to demonstrate suppression of LH at a level of < 4 mIU/mL at 30 minutes after GnRHa stimulation in a majority of subjects ($\geq 80\%$) who are treated with leuprolide acetate 45 mg in an injectable suspension. Descriptive outcomes for the primary and secondary efficacy variables will be used to evaluate the efficacy of this treatment.

If suppression in $\geq 85\%$ of the first 16 subjects to be evaluated at Month 6 is found, the study will terminate under Part A without the invocation of Part B as a follow-on adaptive dosing schedule. If study termination under Part A occurs, the criterion variable for adaptive change applied to the first 16 patients at six months, namely, percent of patients with < 4 mIU/mL suppression, will *also* function as the primary outcome variable when applied to all patients in the study. As was the case for evaluating adaptive change in design, an absolute descriptive rather than inferential statistical outcome will be used to assess efficacy for the primary outcome variable. Efficacy will be claimed if $\geq 80\%$ of the subjects exhibit < 4 mIU/mL suppression.

If suppression in $< 85\%$ of the first 16 subjects to be evaluated at Month 6 is found, the study will be adapted and Part B will be invoked. As would be the case if the study were to terminate with Part A, the percent of subjects with < 4 mIU/mL suppression will serve as the primary outcome variable under Part B. If < 4 mIU/mL suppression in $\geq 80\%$ of the patients in the study at Visit 11 (Month 21) is found, efficacy will be claimed.

